The primary outcomes will be PCWG and 7-day point prevalence abstinence at 26 weeks after the target quit date. Food intake (secondary outcome) will be measured via 24-hour food recalls conducted over 3 consecutive days at pre-treatment, mid-treatment, end of treatment, and follow-up. Mediating mechanisms (e.g., alternative reinforcers, relative reinforcing value of food, food reward, and food cue-induced craving) will be assessed before, during, and at the end of treatment (week 8). Potential moderators include gender, depression symptoms and weight concerns.

1.2 *Background - Neuroimaging Sub-Study*

The parent randomized clinical trial of behavioral activation intervention (BAS+) integrates Behavioral Economic Theory and cognitive neuroscience research. The basic premise is that smoking cessation produces a reward dysregulation that increases the reward value of other reinforcers, such as highly palatable foods. Because food is a readily available reinforcer --and palatable foods increase in their incentive salience after quitting-- food cue-elicited reactivity in the brain's reward system would increase with smoking cessation. Food reward and reinforcing value also increases in the context of cessation leading to increased food intake. Cessation-induced increases in food reward are paralleled by decreases in the ability to control the consumption of palatable food. Research by our group and others shows that cessation impairs aspects of executive function that are critical to self-control. Abstinence reduces engagement of brain regions essential for cognitive control and individuals with lower levels of response inhibition are less able to resist palatable foods, and are more vulnerable to overeating. Working memory is important to keep goals in mind and for efficient use of behavior change tools, yet it can be depleted by efforts to manage cravings. This will be the first study to integrate these concepts and to explore brain mechanisms underlying a behavioral activation intervention (BAS+) to promote smoking cessation and mitigate PCWG.

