3.1 General Design - Parent (Main) Study

This is a randomized clinical trial of the efficacy of BAS+ plus TN compared to SC plus TN in treatment-seeking smokers. After completing an Intake Visit (~week -3), eligible smokers will be randomized (stratified by nicotine dependence, BMI and gender) to participate in 8 individual sessions of BAS+ or SC over a 10-week treatment period with two sessions prior to the target quit date (weeks -2, -1) and six sessions post-target quit date (TQD [week 0] and weeks 1, 2, 4, 6, and 8). Standard, 8-week; open-label TN will begin on the TQD. Moderators will be assessed pre-treatment. Mediating mechanisms will be assessed before, during, and at the end of treatment (EOT, week 8). Smoking will be assessed by self-report and biochemically confirmed (Carbon Monoxide [CO] < 5 or absence of Urine Cotinine) at all in-center visits (for CO ONLY) after quitting, at EOT (week 8), and at the 12- and 26-week follow-ups. Weight will be assessed at these same time points. Food intake will be measured by three consecutive days of 24-hour food recalls at Baseline [week -2] and 4-, 8-, and 12- and 26-weeks post-TQD. Smoking cessation and PCWG are the primary outcomes and food intake is a secondary outcome at 26-weeks post-TQD. Consistent with intent-to-treat (ITT) analyses, we will measure smoking cessation and weight gain in the full sample at the 26-week follow-up, evaluating a smoking status by treatment interaction for the PCWG analysis.

Time points (i.e. study weeks) displayed in Figure

[figure not shown]
CONFIDENTIAL

This material is the property of the University of Pennsylvania. Do not disclose or use except as authorized in writing by the study sponsor

1 and included within the Study Procedures Section represent approximations. Participants will follow a study schedule similar to that designated in Figure 1 and the Study Procedures, but will be permitted a degree of flexibility based on the maximum/minimum amount of time allowed between each time point established by the Principal Investigator. If a participant is unable to attend an in-person visit within the permissible window of time allotted between time points, counseling and applicable study measures may be completed/collected via telephone. In-person completion of the Intake and Baseline Visits are considered mandatory for study participation.

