6.5.6 Outcomes

Weight: Weight (primary outcome) will be measured by a physician's scale (pounds) at the beginning of every in-person visit. Participants will be wearing light clothing without shoes. Pre-cessation weight will be computed as the average of weights at the Intake and Baseline Visits prior to any change in smoking behavior. Weight change from Baseline to the 26-week follow-up will serve as a primary weight outcome variable.

Food Intake (24-Hour Dietary Recalls): Food intake (secondary outcome) will be assessed via 3 telephone-administered, 24-hour dietary recalls during the week after (or near) the Baseline, Mid-Treatment 3 (week 4), End of Treatment (week 8) and the 12-week and 26-week follow-up visits (n=15). A trained member of the research staff will use a multi-pass method with an interactive computerized software program, the ASA24® (Automated Self-Administered 24-hour Recall), to determine total kcal/day (outcome variable). The ASA24® was created by investigators at the NCI. Three recalls are considered optimal for assessing dietary intake, especially when weekend and weekdays are assessed, as we propose to do when possible. If participants are unable to complete a scheduled recall over the telephone or are onsite for a scheduled visit, participants may be asked to complete a 24-hour dietary recall with the research staff in-Center. Comparable accuracy can be achieved when administered in-person and over the telephone. Food recalls are widely used, reliable and valid, assessing kcals/day within 10% of actual dietary intake measured under laboratory observation and by doubly labeled water.

Changes in food intake (kcals) from baseline to week 12 will serve as an outcome for the microbiome sub-study.

Smoking Cessation (CO, Urine Cotinine, and Saliva Cotinine): Smoking abstinence (primary outcome) will be assessed and biochemically verified at EOT (week 8), at 12 and 26 weeks after the target quit date. The primary smoking outcome variable will be 7-day point prevalence abstinence (no smoking, not even a puff, for at least 7 days prior to the assessment) biochemically verified by CO < 5 ppm or Urine Cotinine assessment at a sensitivity of 100 ng/mL at EOT (week 8) and Follow-Up 1 and 2 visits (Week 12 and Week 26). Smoking status will also be biochemically confirmed by saliva cotinine < 15ng/ml at the 12- and 26-week follow-up.

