6.7 Sample Size Determination- Parent (Main) Study

For **Aim 1** we hypothesize that BAS+ vs. SC will have higher smoking abstinence rates and less PCWG at the 26-week follow-up (primary outcomes). Power calculations were all approximated as t-tests or z-tests, and conducted using PASS Software (Power and Sample Size, NCSS Software, Kaysville, UT), Bonferroni corrected for two primary outcomes ($p=.025$). Proportions of abstinent and smoking subjects will be compared using the log of the odds-ratio, which has a known variance. Informed by smoking cessation counseling plus TN research, we anticipate that the 6-month abstinence rate will be 13% in the SC (control) group and 25% in the BAS+ group (consistent with a persistent effect of BAS+ after the discontinuation of TN). A sample of 213 per group provides 82% power to detect this 12% difference in quit rates at 6 months. This represents a clinically meaningful effect and corresponds to a small effect size ($\delta=.15$). For PCWG, we will include all participants in the analysis, while testing a smoking status x treatment interaction. Informed by epidemiological and clinical studies of PCWG, we will have 80% power to detect a 6 pound (2.72 kg) difference in PCWG between BAS+ and SC, using the interaction term. We expect BAS+ vs. SC will have less post-cessation food intake (secondary outcome) at the 26-week follow-up. We have 80% power to detect a 320 kcal/day difference between the two groups ($p = .05$). In light of these considerations (i.e., 213 subjects per arm; total 426) and an attrition estimate of 15% across accrual, we will recruit a total of 245 subjects to each arm for a total of 490 subjects (~500).

For **Aim 2**, we hypothesize that BAS+ vs. SC, will increase alternative reinforcers, and reduce food reward, the RRVF, and food cue-induced craving. These changes, in turn, will predict less food intake and PCWG, and greater smoking abstinence at the 26-week follow-up. Using structural equation modeling, we will test the treatment effect on the slope of the mediators versus time, with pre-quit values representing the intercepts. We will examine the proportion of

CONFIDENTIAL

This material is the property of the University of Pennsylvania. Do not disclose or use except as authorized in writing by the study sponsor

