6.10 Statistical Methods - Parent (Main) Study

Prior to the analyses, we will: (a) screen the data for data-entry errors, (b) check for outliers, and (c) assess the extent and type of missing data, and select the most appropriate method for dealing with the missing data (e.g., multiple imputation, all available data). We will create all summary scores needed for analysis, and check that distributional assumptions are met. We will assess for participation biases, attrition differences and treatment adherence (controlled for in primary analyses) across treatment arms. Main effects and moderated effects analyses will be conducted using Stata software (StataCorp, College Station, Texas) and mediation analyses will be evaluated using Mplus software 7.2.

Aim 1 will evaluate smoking abstinence (point-prevalence, binary outcome) and PCWG (kg weight gain, continuous outcome) in the context of a longitudinal model with categorical and continuous predictor variables. We will use generalized linear models fitted with random effects using Generalized Estimating Equations. We will specify the logistic model for the binary abstinence outcome, and Gaussian weight gain outcome. Models will include treatment assignment, time point, adherence measures, and covariates related to the outcome in

CONFIDENTIAL

This material is the property of the University of Pennsylvania. Do not disclose or use except as authorized in writing by the study sponsor

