preliminary analyses. Comparisons are all between-subjects. We will test for interaction between treatment and time point using the Wald Chi-square, and estimate a common odds-ratio across time points if they show no evidence of differing across time. The primary hypothesis will be tested using the z-score corresponding to treatment assignment at EOT, and at 12- and 26-weeks post quit, with the primary test of hypothesis 1a at 26-weeks post-TQD. Consistent with ITT analyses, we will measure smoking cessation and weight gain in the full sample at the 26-week follow-up, evaluating a smoking status (days x rate) by treatment interaction for the PCWG analysis (H.1.b.). The **exploratory aim** will evaluate variables that modify the effect of treatment on smoking cessation and PCWG. We will enter interaction terms (e.g., treatment x depression) to the models generated for Aim 1. The interactions will be retained if the z-score is significant ($p<0.05$). We will focus first on EOT, then the 12-week and 26-week follow-up time points, and finally the combined effect across time point.

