Aim 1: Identify effects of BAS+ (vs SC) treatment on food related neural activity and behavior: These comparisons are all between subject, and will be analyzed using mixed models regression (xtmixed, StataCorp, Texas). The model predictors will include a binary indicator for group (BAS+ vs. SC). The hypothesis will be tested using the z-score corresponding to the main effect of group. Covariates can be included in the model to control error (sex, BMI, nicotine dependence, age, weight concerns), although we do not expect to make large gains for adding subject-level controlling variables in a mixed model.

Aim 2: Evaluate the relative contribution of these neural processes to post-cessation caloric intake: Our outcome variable is average daily calories based on food recalls. The first comparison (pre vs. post-treatment) is within-subject, and will be analyzed using mixed models regression with subject specific random effects. As before, we include a binary predictor for condition, a categorical indicator for serial day, and we will test using the z-score corresponding to condition. For testing candidate mediators, we will again model calories using mixed models, entering variables as time-varying (condition varying) predictors, along with subject specific random effects. Finally, we will build the larger model, looking for confounding that represents potential mediation. For this purpose, we will use regression-based multi-equation path models. Path Analysis partitions a directly measured bivariate relationship, for example, between abstinence and calories ingested, into direct and indirect causal paths, to tease apart the important components mediating the response. We will deem that mediation has occurred when a relationship between abstinence and food intake accounted in full, or in part, by one or more of the intervening variables (BOLD signal change or subjective responses in cessation vs. smoking). We will assess the strength of the indirect effects through confidence intervals, evaluate the proportion mediated (i.e., partial or complete mediation), and determine significance with Delta method standard errors. To assess the level of mediation for a pathway, we will estimate the ratio of the indirect effect to the total effect (i.e., effect proportion mediated $\beta_{\text{indirect}}/\beta_{\text{total}}$).

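### The primary models leave their covariates to an undefined outcome-based screen instead of fixing the three randomisation stratification factors and pre-cessation weight

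*Combined protocol and SAP*

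**What the plan says.** There are two primary outcomes. Section 1.1 states: "The primary outcomes will be PCWG and 7-day point prevalence abstinence at 26 weeks after the target quit date". Section 6.7 sets the test level at 0.025 each, "Bonferroni corrected for two primary outcomes".

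On the design, section 3.1 says that "eligible smokers will be randomized (stratified by nicotine dependence, BMI and gender"). It gives no cut-points for nicotine dependence or BMI.

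On the analysis, section 6.10 (Aim 1) covers both outcomes, with a logistic model for abstinence and a Gaussian model for weight gain. The terms are given in one sentence: "Models will include treatment assignment, time point, adherence measures, and covariates related to the outcome in" preliminary analyses. Treatment, time point and adherence are therefore fixed, and everything else is chosen by association with the outcome. The section does not list candidates, name a test or threshold, or say whether the screen is done before treatment codes are seen.

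Section 6.5.6 defines a baseline for the weight outcome, "Pre-cessation weight will be computed as the average of weights at the Intake and Baseline Visits", but 6.10 does not make it a model term. The only place that names the stratification variables as covariates is section 6.11, for the neuroimaging sub-study, and there they are optional: "Covariates can be included in the model to control error (sex, BMI, nicotine dependence, age, weight concerns"). In the parent-study analysis, gender is named only as an exploratory moderator.

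**The concern.** The usual rule is to analyse as randomised: factors that were balanced by design go into the primary model. If a balanced factor predicts the outcome and is omitted, the model's standard error ignores the balance. It is then too large, and the test rejects less often than its nominal level.

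The plan's rule also leaves the primary model undefined until data are in hand. Two analysts following 6.10 could fit different models and both be in line with it. For weight, this changes the precision of the estimate. For abstinence it also changes the quantity estimated, because an odds ratio conditional on covariates differs from the marginal one even when the arms are perfectly balanced.

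At stake are the reproducibility of the headline estimates and, under some choices, part of the precision that stratification makes available.

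**Working it through.** **1. The plan's own power figure.** Inputs from 6.7: 13% vs 25% abstinent, 213 per group, alpha 0.025. Sidedness is not stated; two-sided is assumed (z = 2.241). Pooled z-test:

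- Numerator: 0.12 × √213 − 2.241 × √(2 × 0.19 × 0.81) = 0.508
- Denominator: √(0.13 × 0.87 + 0.25 × 0.75) = 0.548
- Power: Φ(0.508 / 0.548) = Φ(0.926) = 82.3%

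The stated 82% reproduces. One-sided 0.025 would give 88.7%, which does not fit. The calculation uses no covariates, so the adjustment set does not affect it.

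**2. Weight: fitted versus left out entirely.** The documents give no strength of association, so the fraction of variance explained by the factors, R², is assumed. Starting from 80% power, power = Φ((2.241 + 0.842)/√(1 − R²) − 2.241). The equivalent size per arm is 213/(1 − R²).

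| Assumed R² | Power if fitted | Gain (points) | Equivalent n per arm |
|---|---|---|---|
| 0.05 | 82.2% | 2.2 | 224 |
| 0.10 | 84.3% | 4.3 | 237 |
| 0.15 | 86.5% | 6.5 | 251 |

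This compares full adjustment with none. The plan's rule lies between the two, which is why step 3 is needed.

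**3. Against a screening rule.** Simulation: 4,000 trials per setting, 426 participants, three balanced binary strata, blocked 1:1 allocation within the eight cells, one week-26 outcome, two-sided 0.025. The strata are omitted, always fitted, or kept only if p<0.05. The p<0.05 threshold is assumed, since the plan gives none.

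| Outcome and assumed strength | Power omitted | Power always fitted | Power screened |
|---|---|---|---|
| Abstinence, OR 1.0 per stratum | 82.2% | 82.5% | 82.2% |
| Abstinence, OR 1.5 | 83.1% | 84.2% | 83.9% |
| Abstinence, OR 2.0 | 83.5% | 85.2% | 85.1% |
| Abstinence, OR 3.0 | 83.5% | 87.2% | 87.2% |
| Weight, R² 0.05 | 81.6% | 83.0% | 83.1% |
| Weight, R² 0.10 | 80.4% | 84.0% | 84.0% |
| Weight, R² 0.20 | 82.9% | 88.7% | 88.7% |

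Always fitting beats the screen by about 0 to 0.3 points. Simulation error is about 0.6 points per figure, but the comparisons are paired.

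**4. Type I error, nominal 2.5%.** With prognostic strata omitted, the weight test rejects 2.3%, 1.8% and 1.4% of the time at R² 0.05, 0.10 and 0.20. The abstinence test gives 1.8-2.7%, without a clear trend. With the strata fitted or screened, both outcomes give about 2.3-2.9%. Simulation error is about 0.25 points.

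**5. The odds ratio.** The marginal odds ratio for 25% vs 13% is (0.25/0.75)/(0.13/0.87) = 2.23. Keep those marginal rates, give each of the three balanced strata the same odds ratio, and solve for each arm's intercept on the logit scale. The conditional odds ratio is exp(difference of intercepts):

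- OR 1.5 per stratum: exp(−1.129 + 1.946) = 2.26
- OR 2.0 per stratum: exp(−1.185 + 2.030) = 2.33
- OR 3.0 per stratum: exp(−1.304 + 2.212) = 2.48

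The same trial result can therefore be reported as 2.23 or as something larger, depending on which covariates pass the screen.

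**The case against.** The strongest reply is that the plan's rule tends to protect precision. A stratification factor helps only if it is related to the outcome, and that is the kind of covariate 6.10 says it will admit. A reader might infer from sections 3.1 and 6.10 that both primary tests lose power. The documents do not support that: they do not say the factors will be ignored, and step 3 shows almost no loss under a p<0.05 screen. This part of the reply stands. It is not a full answer, because the plan states no threshold and the simulation screened only the strata, not baseline weight.

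A reader might also infer that covariates could be re-chosen after the treatment result is known, inflating false positives. Section 6.10 speaks only of preliminary analyses, which suggests a step before the treatment test. The wording leaves room for re-selection but does not describe it, and screening at p<0.05 kept type I error near nominal.

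Baseline weight is partly handled, since the outcome is change from pre-cessation weight. Leaving it out of a change-score model is not an error, though fitting it may add precision.

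Finally, the models do not adjust only for screened covariates, because time point and adherence are fixed terms. Nor must both outcomes succeed together, because alpha is split between them.

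**Conclusion.** The point holds as a prespecification defect. The design stratifies on three factors, and the primary analysis uses a different, outcome-driven rule that it does not define. The adjustment set and the conditional odds ratio for abstinence are therefore open until the data are seen. Omitting a prognostic stratum would make the test conservative.

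The power consequence is small or conditional. It is about 0 to 0.3 points against a p<0.05 screen of the strata. For weight it is about 2 to 6 points from 80%, and only if factors explaining 5-15% of the variance were left out entirely. The plan's 82% is unaffected.

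These sizes rest on assumed association strengths, balanced strata, an assumed threshold and a single week-26 outcome. The repeated-measures model and the smoking status by treatment interaction, on which the plan's 80% power for weight is based, were not simulated.

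The change should be made, for reproducibility first and precision second. Adjustment for adherence, which is measured after randomisation, is a separate issue.

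**What to change.** In section 6.10, Aim 1, replace the last clause of the model sentence (the part after the adherence measures) with:

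*Both primary models include the three stratification factors (nicotine dependence, BMI, gender), in the form used at randomisation. The weight model also includes pre-cessation weight (mean of Intake and Baseline). No other covariate is selected using outcome data; models with further prespecified baseline covariates are sensitivity analyses.*

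State the categories used for nicotine dependence and BMI at randomisation, since section 3.1 gives no cut-points.

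The cost is wording only. The dependence score, height, weight and gender are recorded at Intake. The second weight is taken at the Baseline Visit before the first counselling session (6.2.3), so it precedes treatment. No data, visits or participants are added. This text leaves the adherence term as it is; that needs its own decision.

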4.2 Accrual - Parent (Main) Study

We will enroll ~625 participants (i.e., provide consent) to achieve a sample of ~340 who enter treatment (i.e., randomized) and remain enrolled through the 26-week assessment. To achieve this goal over a ~44-month enrollment period, we will complete 55 telephone screens monthly to obtain 25 smokers who meet criteria. Of these smokers, we expect ~15 to attend the Intake Visit, and ~10 per month to be confirmed eligible to be randomized after completing the Intake Visit.

In order to increase retention throughout the study we will: (1) educate subjects about the benefits of participation and the knowledge gained from the study; (2) schedule sessions at times convenient for participants; (3) provide reminder calls; and (4) provide payment for completion of all study visits. As is the convention in smoking cessation trials, smokers who are lost to follow-up will be included in the analysis and counted as smokers.

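### The 80% power for a 6 lb weight difference fits a yes/no smoking status, but the analysis section defines smoking status as days x rate, so the stated power does not describe the specified term

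*Combined protocol and SAP*

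**What the plan says.** Section 6.7 sets alpha at .025 for each of two primary outcomes, abstinence and PCWG at week 26. For PCWG it keeps all participants, tests a smoking status by treatment interaction, and states: "we will have 80% power to detect a 6 pound (2.72 kg) difference in PCWG between BAS+ and SC, using the interaction term". It does not define the scale of smoking status. It does speak of abstinent and smoking subjects, and its exploratory paragraph uses 54 and 28 abstinent participants.

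Section 6.10, Aim 1, describes the same analysis as "evaluating a smoking status (days x rate) by treatment interaction for the PCWG analysis". It gives no time window, no scaling, and no link to the verified 7-day point-prevalence outcome in 6.5.6. Section 3.1 names the interaction without defining smoking status.

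Section 6.10 also says that the primary hypothesis is tested with the z-score for treatment assignment, with hypothesis 1a tested at 26 weeks. It attaches the label H.1.b to the PCWG interaction, although in section 2.1 weight gain is H1a and H1b is cessation.

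On dropouts, section 4.2 says that "smokers who are lost to follow-up will be included in the analysis and counted as smokers".

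**The concern.** The two sections appear to use different variables under one name. With a yes/no status, the interaction coefficient is a difference in kg: how much more BAS+ changes weight gain in abstainers than in smokers. With days x rate it is a difference in slopes, in kg per unit smoked. If so, the only power figure for the weight co-primary belongs to a test other than the one specified.

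The choice also affects validity. A straight line in consumption fits poorly if weight gain changes mainly at the point of abstinence. If the arms then differ in how many people abstain, the misfit differs by arm and can look like a treatment interaction. Because window and scale are open, they could also be settled after the data are seen.

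**Working it through.** **Inputs.** From 6.7: 213 per arm; abstinence as in "6-month abstinence rate will be 13% in the SC (control) group and 25% in the BAS+ group"; 54 BAS+ and 28 SC abstainers, hence 159 and 185 smokers; effect 2.72 kg; alpha .025; and "Power calculations were all approximated as t-tests or z-tests". The SD of 3.5 kg is given in 6.7 for the exploratory interaction among abstainers. Using it for the co-primary figure, and for smokers too, is an assumption. Sidedness is not stated in 6.7; two-sided is used here.

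**Checks on the inputs.**
- Quit rates: the plan says "A sample of 213 per group provides 82% power to detect this 12% difference in quit rates at 6 months". With pooled p = .19, SE0 = sqrt(2 × .19 × .81/213) = .0380 and SE1 = sqrt((.13 × .87 + .25 × .75)/213) = .0376. Power = Φ((.12 − 2.241 × .0380)/.0376) = 82.3%. Two-sided .025 is confirmed.
- Exploratory SE: 3.5 × sqrt(2/27 + 2/14) = 1.63, as stated.

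**Reproducing the PCWG figure with a yes/no status.**
- SE = 3.5 × sqrt(1/54 + 1/28 + 1/159 + 1/185) = 0.899 kg.
- 2.72/0.899 = 3.03; power = Φ(3.03 − 2.24) = 78.4%.
- Difference detectable with 80% power: (2.241 + 0.842) × 0.899 = 2.77 kg, or 6.1 lb.

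Other readings with the same inputs do not match: 85.7% at alpha .05; 86.3% for a comparison within abstainers at .025; over 99.9% for an overall treatment effect.

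**The days x rate term.** No closed form follows from the documents, so this was simulated: 213 per arm, 25% and 13% abstinent, SD 3.5 kg, weight change regressed on treatment, status and their product, robust SE, two-sided alpha .025, 2,000 to 3,000 runs per scenario. Two sets of assumptions, none of them in the documents, were used:
- Set A: smokers average 5 to 12 cigarettes/day, CV .5 to .9, past 7 days.
- Set B: smokers average 14 cigarettes/day, CV .4 to .6, smoking on all 7 days or on 1 to 7 days.

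| Scenario | Days x rate rejects | Yes/no rejects |
|---|---|---|
| BAS+ lowers gain 2.72 kg in abstainers; abstainers otherwise gain 3–4.5 kg more (A) | 4–26% | 76–79% |
| Same, abstainers gain 3–6 kg more (B) | 4–34% | 77–80% |
| Same, abstainers gain no more than smokers (A) | 29–55% | about 78% |
| No effect on weight within status; abstainers gain 3–4.5 kg more (A) | 7–15% | about 2–4% |
| Same, 3 to 6 kg more (B) | 7–9% rising to 17–21% | 2.5–3.6% |
| As the row above, quit rates equal at 19% (B) | 2.0–3.6% | near nominal |

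**Mirror case.** Let weight be linear in consumption, with a 3 to 4.5 kg gap between abstainers and the average SC smoker and no treatment effect given consumption. If BAS+ smokers smoke 20% less than SC smokers (assumed), the yes/no test rejects about 6 to 12% of the time; at 40% less, about 19 to 40%. Days x rate stays at about 2 to 4%. With no reduction, both are near nominal.

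**Current sample target.** Sections 3.4 and 4.2 now aim for about 340 participants, against 426 in 6.7. If that means 170 per arm analysed, the yes/no SE is 0.899 × sqrt(213/170) = 1.006 kg and power is Φ(2.72/1.006 − 2.241) = 68%. Using 25% and 13% of 170 directly gives SE 1.011 kg and 67%.

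**The case against.** Several points on the other side stand.

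- The yes/no reading of 6.7 is inferred. The section does not define status, and the match depends on the carried-over SD (at SD 3.0 or 4.0 kg the same formula gives 90% or 66%). Even so, a coefficient stated in pounds cannot be a days x rate slope.
- A reader might infer that days x rate inflates false rejection as such. The documents do not support this. It takes a departure from linearity, such as a step at abstinence, together with arms that differ in quit rate or consumption. Unequal quit rates are the trial's own hypothesis; the shape of the weight effect is nowhere stated.
- A reader might infer that yes/no status is the safe choice. The mirror case shows that it is not uniformly safer.
- A reader might infer that participants lost to follow-up make days x rate impossible to score. More exactly, no scoring rule is given. Section 6.10 leaves the missing-data method open, including multiple imputation. Participants lost at week 26 will generally lack a weight under either definition.
- It is not settled that the interaction is the co-primary weight test, because 6.10 also points to the treatment z-score. The error rates above bear on the .025 allocation only if the interaction is that test. The mismatch remains either way, since 6.7 ties its power to the interaction.
- The simulations use one time point and ordinary regression, whereas 6.10 plans a longitudinal GEE with adherence and covariates. They show direction and rough size, not the operating characteristics of the planned model.

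**Conclusion.** The point holds as a mismatch between 6.7 and 6.10. Given SD 3.5 kg and two-sided .025, the stated 80% for 6 lb is the power of an abstinent/smoking interaction (78.4%), not of the days x rate interaction that 6.10 specifies. For a 2.72 kg benefit confined to abstainers, the specified term has about 4 to 55% power under the assumed smoking distributions.

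The error-rate part is conditional. Rejection of about 7 to 15% against a nominal 2.5% needs a 3 to 4.5 kg step in weight gain at abstinence and quit rates of 13% and 25%. With equal quit rates and equal consumption among smokers, or an effect truly linear in consumption, the term stays near nominal. The documents give no ground for calling the planned test invalid outright, nor for ruling that one definition is statistically correct. They do require that a single one be chosen, defined and powered.

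**What to change.** Use one definition of smoking status for the PCWG interaction in 6.7 and 6.10. Either:

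1. state in 6.10 that it is verified 7-day point-prevalence abstinence (yes/no) at week 26, which is what 6.7 appears to have powered, and make days x rate a supportive analysis; or
2. keep days x rate, define its window, its scale and its scoring for participants lost to follow-up, and delete the 6 lb / 80% statement or re-derive it for that variable.

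In both cases, state whether the treatment z-score or the interaction is the co-primary PCWG test, correct the hypothesis label, and restate power for the sample now targeted.

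The cost is wording only, with no new data. Under option 1 the dose information moves to a supportive analysis, and the stated power becomes less favourable: about 67 to 68% for 2.72 kg if 170 per arm are analysed.
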